6.4.3 Retrospective-Modified Overt Aggression Scale (R-MOAS) (Section 12.2)

The R-MOAS was developed to gauge the severity of aggressive behavior (Blader et al., 2009). Parents rate the frequency over the past week of 16 aggressive behaviors in 4 areas: verbal aggression; physical aggression toward others; aggression toward oneself; and destruction or hostile misuse of property. Numeric weighting amplifies the seriousness of more harmful behaviors in the total score. The R-MOAS will be administered at Visit 1, Visit 4, and Visit 6.

6.5 Other Special Tests

The following special tests will be administered in the clinic as per Schedule of Events during the Screening Period:

6.5.1 MINI-KID (Section 12.7)

The MINI-KID is designed to be used for children aged 6 to 17 years old, and has been shown to have substantial to excellent concordance with the diagnosis of ADHD, among other Axis I psychiatric disorders (Sheehan et al., 2010; Leffler et al., 2015). The interview can take from 15 to 50 minutes, and can be given to parents or children, together or separately (Leffler et al., 2015). All the modules will be administered except for modules R, S, T, U, V and W. This assessment will be administered at Visit 1.

6.5.2 Vitiello Aggression Scale (Section 12.8)

The Vitiello Aggression Scale is a 10-item rating scale that uses a cluster analysis to categorize aggression into 2 subtypes, predatory (or planned) and affective (or impulsive) (Vitiello et al., 1990). This assessment will be administered at Visit 1.

6.5.3 Edinburgh Handedness Inventory (Section 12.9)

The Edinburgh Handedness Inventory is a measurement scale designed to establish hand dominance. The shorter version, 10-item inventory is a self-report questionnaire on everyday common activities such as writing, drawing, throwing and using utensils. Subjects place 1 or 2 "+" marks under "left" or "right," indicating strength of preference for each activity; 2 "++" are to be used if the individual "would never try to use the other hand unless absolutely forced to" for the given function (Oldfield, 1971). This assessment will be administered at Visit 2.

7 STATISTICAL METHODS

7.1 General Notions

Tabular summaries of the data collected during the study will provide a general description of the subjects studied and an overview of the treatment effect on brain functioning, GABA and Glu levels, PK, and safety results. Data from all sites will be combined in the computation of these summaries. Correlations between changes in neuronal activation and neurotransmitter concentrations will be analyzed. Continuous variables will be summarized using descriptive statistics (number of subjects, mean, standard deviation [SD], median, and minimum and maximum). Categorical (nominal) variables will be summarized by reporting the frequency and percentage of subjects in each category.

In addition to tabular summaries, subject data listings, as specified in Sections 16.2 and 16.4 of ICH Guidance E3, will be provided. Analysis processing will be performed before the database is released. Statistical programming and analyses will be performed.

Complete details of the statistical analysis will be provided in a separate Statistical Analysis Plan (SAP), which will be written, finalized, and approved prior to the database lock and will be

included in the Clinical Study Report (CSR) for this protocol. Any deviation from the statistical plan will be documented and described in the final report. If changes to principal features stated in the protocol are required, these will be documented in a protocol amendment. The final SAP will take into account any amendment to the protocol.

7.2 Handling of Dropout or Missing Data

No imputation will be implemented.

7.3 Analysis Populations

The population of "all enrolled subjects" consists of all those screened subjects who meet the requirements for study participation and have completed the imaging procedures prior to randomization. The population of "all randomized subjects" consists of all those enrolled subjects who complete the Baseline Period including imaging scans, meet the inclusion/exclusion criteria and are randomized. The following populations will be analyzed:

Safety Population: includes all subjects randomized and who received at least 1 dose of study drug.

Completed Population: includes all subjects randomized, who have baseline imaging scans (including the anatomical scan) and post-treatment imaging scans.

PK population: includes all subjects in the safety population who had at least 1 PK sample drawn which had a quantifiable concentration of molindone.

7.4 Demographics

Demographic variables include age, sex, ethnicity, race, height, weight, and medical history at Screening. Tabular summaries of the demographic/baseline variables will be presented for the completed and safety populations, except for medical history, which will be summarized for the safety population.

7.5 Subject Disposition

The number and percentage of subjects who completed and discontinued from the study will be summarized in each of the following categories:

- Subjects in the randomized population
- Subjects treated (safety population)
- Subjects in the completed population

The reasons for study discontinuation may include one of the following:

- Subject withdrew consent
- Lost to follow-up
- Lack of efficacy
- Administrative reason
- Adverse event

- Investigator decision
- Failure to follow required study procedures
- Other

Only one reason for study discontinuation will be recorded for each subject.

7.6 Protocol Deviations

Protocol deviations will be presented in listings. If applicable, the number and percent of subjects within each type of protocol deviation will be presented using discrete summary statistics. Protocol deviations may include, but are not limited to:

- Non-compliance with any scheduled study visit
- Compliance with study treatment <80%
- Disallowed concomitant medications
- Non-compliance with study inclusion or exclusion criteria
- Non-compliance with study assessment procedures

7.7 Study Medication Exposure and Compliance

Duration of treatment exposure is defined as the total number of days a subject is exposed to study treatment. This will be calculated for each subject by taking the difference between the date of last dose *minus* the date of the first dose, *plus* 1 (date of last dose – date of first dose +1).

Duration of treatment exposure will also be summarized using descriptive statistics (n, mean, SD, median, minimum, and maximum).

Percent of study drug compliance will be calculated as:

 $\{(D-R)/4*(D_L-D_F)\}*100$, where D=number of tablets dispensed, R=number of tablets returned, D_L =date of last visit (dose) and D_F =date of first visit (dose)

The study medication compliance will be summarized by compliance category (<80%, 80-120%, and >120%) and number of subjects in each compliance category. Study medication compliance will also be summarized as a continuous variable using descriptive statistics (n, mean, standard deviation, median, minimum, and maximum).

Summaries of treatment compliance and exposure will be presented separately for the Titration period, Maintenance period, and combined Titration and Maintenance periods.

8 STATISTICAL ANALYSIS

Both primary and secondary analyses will be based on the completed population.

8.1 Primary Endpoint Analysis

The primary endpoint will be analyzed by assessing the difference in the change in BOLD fMRI contrast related to the aggressive response in the PSAP Task from baseline (Visit 2) to the end of treatment (Visit 5) in each treatment group.

This document is confidential. It contains proprietary information of Supernus® Pharmaceuticals, Inc. Any viewing or disclosure of such information that is not authorized in writing by the Sponsor is strictly prohibited. Such information may be used solely for the purpose of reviewing or performing this study.

8.1.1 *Imaging Analysis*

All functional imaging data will be analyzed using statistical parametric mapping software SPM12 package (Wellcome Trust Centre for Neuroimaging, Institute of Neurology; London, UK), Analysis of Functional Neuroimages (AFNI, NIH, USA) and software developed in-house at [name] lab, by [name], and at Supernus. Additional software that may be used includes FSL (Oxford, Cambridge, UK), Freesurfer (MGH, USA), and Matlab (MathWorks, USA). While performing the PSAP Task, neuronal activation is anticipated in the ACC, ventromedial PFC, amygdala, insular regions, and ventral striatum including nucleus accumbens, etc. Therefore these ROIs will be emphasized during the imaging analysis.

8.1.1.1 PSAP Task

For the PSAP Task data, the analyses will be mainly descriptive and will be assessed as the change in BOLD fMRI contrast associated with the aggressive response at baseline and post-treatment. The primary endpoint may be analyzed by assessing the mean, standard deviation, median, minimum and maximum of the BOLD signal change related to aggression for each treatment group (SPN-810 36 mg group and placebo) and study visit (baseline and Visit 5).

Additional analysis details will be described in the SAP.

8.2 Secondary Endpoint Analyses

8.2.1 Functional Connectivity (Resting State fMRI)

The secondary endpoints for functional connectivity will be the actual z-score, converted from the Fisher's Z-transformation of correlation coefficients, acquired during the rs-fMRI at Baseline (Visit 2) and Visit 5.

The analyses of the resting state data will be exploratory and informative of the connectivity between ROIs of the aggression network. Correlation matrices representing functional connectivity in the aggression network for each resting state scan will be generated at Visit 2 (baseline) and at Visit 5. The correlation values will be converted to a z-score (Fisher's Z-transformation). The descriptive analyses will be performed to assess the z-scores by treatment group (SPN-810 36 mg group and placebo) and visit (baseline and Visit 5).

The mean difference, of the z-scores between two treatment groups (SPN-810 36 mg group minus placebo) and pre- and post-treatment (post- minus pre-treatment) and the associated 2-sided 95% CI of the differences will be reported.

Additional analysis details will be provided in the SAP.

8.2.2 GABA and Glutamate Concentrations

The concentrations of GABA and Glu in the ACC will be obtained during MRS acquisition. The analyses will be descriptive by assessing the statistics for the concentrations of GABA and Glu by treatment group and visit (pre-treatment: Visit 2 fMRI scan and post-treatment: Visit 5). The change from baseline will be defined as the difference in concentration of GABA and Glu between Visit 2 and Visit 5 for each treatment group. The 2-sided 95% CI for the mean difference between treatment group and pre- and post-treatment will be also examined.

8.3 Safety Analysis

Evaluation of safety will be performed for the safety population. Safety data that will be evaluated include concomitant medications, AEs, clinical laboratory results, vital signs, ECGs, and findings from the physical examinations. The occurrence of neurological side effects will be assessed by looking at any worsening in scores from Visit 1 to the end of the study visit for each of the Simpson-Angus Scale, Barnes Akathisia Rating Scale, and AIMS. Suicidal ideation and suicidal behavior will be measured by the C-SSRS.

All summary tables related to safety analyses will use the safety population.

8.3.1 Adverse Events

AEs will be classified into standardized medical terminology from the verbatim description (Investigator term) using the Medical Dictionary for Regulatory Activities (MedDRA). AEs will be summarized using discrete summaries at the subject and event level by system organ class and preferred term for each group of doses. Similarly, treatment-emergent AEs will be summarized by severity and relationship separately. Verbatim description and all MedDRA level terms, including the lower-level terms, for all AEs will be contained in the subject data listings.

All AEs occurring throughout the study period will be recorded. Treatment-emergent AEs (TEAEs) will be collected starting after the baseline fMRI scan and after the first dose of study medication (after Visit 3) to the end of the study. These AEs include those that emerge after the fMRI procedures and during treatment or worsen in severity during treatment. These AEs will be tabulated, listed, and analyzed.

Separate TEAE incidence tables will be presented for the 2 treatment groups. The incidence rates for all SADRs will also be summarized as described for all TEAEs.

In addition, these same tables will be presented by treatment period (Titration, Maintenance, and combined Titration and Maintenance periods). For the combined Titration and Maintenance periods, the incidence of TEAEs will also be presented by highest severity reported and the dose of study medication at first occurrence. Listings (and tabular summaries, if warranted) of deaths, other SAEs, and other significant TEAEs, including TEAEs resulting in treatment discontinuation, will be provided.

8.3.2 Laboratory Values

Clinical laboratory values will be summarized by visit and by treatment group using descriptive statistics for hematology, chemistry, and urinalysis. For quantitative laboratory parameters, both actual values and change from Baseline values will be summarized.

Laboratory test results will be assigned a low, normal, high (LNH) classification according to whether the values were below (L), within (N), or above (H) the laboratory parameters' reference ranges provided by the central laboratory. Within-treatment comparisons will be based on 3 x 3 tables (shift tables) that, for a particular laboratory test, compare the LNH classification at baseline to the LNH classification at visit. Listings of all abnormal laboratory values by subject (i.e., those with L or H classification) will be provided.

8.3.3 Vital Signs, Height, Weight, and BMI

Vital signs will be summarized by the visit and by treatment group using descriptive statistics. Both actual values and changes from the baseline to final visit will be summarized. Descriptive summary statistics (mean, SD, median, and range) for vital sign data, height, weight, and BMI will be evaluated.

8.3.4 ECG Results

Tabular summaries of the quantitative ECG parameters and the overall ECG findings (normal, abnormal not clinically significant, or abnormal clinically significant) will be presented. The QT will be corrected using Fridericia's method.

ECG results will be summarized by visit and by treatment group using descriptive statistics (for quantitative ECG parameters) and frequency tables (for qualitative ECG parameters, including the overall ECG finding). For quantitative ECG parameters, both actual values and change from Baseline values will be summarized.

8.3.5 Physical Examinations

Findings from the physical examinations will be listed for each system or area examined.

8.3.6 Concomitant Medications

Concomitant medications will be assigned an 11-digit code using the World Health Organization Drug Dictionary (WHO DD) drug codes. Concomitant medications will be further coded to the appropriate Anatomical-Therapeutic-Chemical (ATC) code indicating therapeutic classification. A tabular summary of concomitant medications by drug class will be presented.

8.3.7 *C-SSRS*

C-SSRS outcomes will be summarized using number and percent of subjects by categories for suicidal ideation only, suicidal behavior only, and suicidality (ideation and behavior combined). The summary will be presented by treatment group. The proportion of subjects in each treatment group will be compared with the proportion of subjects in the placebo group using Fisher's exact test or chi-square test as appropriate.

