4.1.2 Exclusion Criteria

- 1. Body mass index (BMI) ≥99th percentile.
- 2. Current or lifetime diagnosis of epilepsy, major depressive disorder, bipolar disorder, schizophrenia or related disorder, personality disorder, Tourette's disorder, fetal alcohol syndrome, or psychosis not otherwise specified.

- 3. Currently meeting DSM-5 criteria for autism spectrum disorder, pervasive developmental disorder, obsessive-compulsive disorder, post-traumatic stress disorder, or intermittent explosive disorder.
- 4. Use of anticonvulsants including carbamazepine and valproic acid, antidepressants, mood stabilizers including lithium, benzodiazepines, cholinesterase inhibitors, or any drug known to inhibit or induce CYP2D6 activity within 2 weeks before the Treatment Period.
- 5. Use of herbal supplements within 1 week prior to Treatment Period.
- 6. Known or suspected IQ <70.
- 7. Unstable endocrine or neurologic conditions that confound the diagnosis or are a contraindication to treatment with antipsychotics.
- 8. Suicidality, defined as either active suicidal plan/intent or active suicidal thoughts in the 6 months before the Screening Visit or more than 1 lifetime suicide attempt.
- 9. Pregnancy, breastfeeding, or refusal to practice contraception during the study (for female subjects of childbearing potential and sexually active males).
- 10. Major visual impairment.
- 11. Documented hearing impairment ≥25 dB loss in either ear and or cochlear implants.
- 12. Known history of implanted brain stimulator, vagal nerve stimulator, ventriculoperitoneal shunt, cardiac pacemaker, orthodontic braces, or implanted medication port.
- 13. Pre-existing medical or psychological conditions that preclude being in the scanner (e.g., claustrophobia, morbid obesity, or marked anxiety about the procedure).
- 14. Substance or alcohol use during the last 3 months.
- 15. Urine drug test at screening that is positive for alcohol or drugs of abuse.
- 16. Known allergy or sensitivity to molindone hydrochloride.
- 17. Lack of IA symptoms due to current medication treatment.
- 18. Any condition that in the opinion of the Investigator or the Sponsor would prevent the subject or the subject's caregiver from participating in the study or complying with the study procedures.
- 19. Use of an investigational drug or participation in an investigational study within 30 days prior Visit 2.

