12.6 Columbia-Suicide Severity Rating Scale (C-SSRS)

12.6.1 C-SSRS, Children's Baseline/Screening

COLUMBIA-SUICIDE SEVERITY RATING SCALE (C-SSRS)

Children's Baseline/Screening

Version 6/23/10

Posner, K.; Brent, D.; Lucas, C.; Gould, M.; Stanley, B.; Brown, G.; Fisher, P.; Zelazny, J.; Burke, A.; Oquendo, M.; Mann, J.

Disclaimer:

This scale is intended to be used by individuals who have received training in its administration. The questions contained in the Columbia-Suicide Severity Rating Scale are suggested probes. Ultimately, the determination of the presence of suicidal ideation or behavior depends on the judgment of the individual administering the scale.

Definitions of behavioral suicidal events in this scale are based on those used in The Columbia Suicide History Form, developed by [name] and [name], Conte Center for the Neuroscience of Mental Disorders (CCNMD), New York State Psychiatric Institute, [name]. (Oquendo M. A., Halberstam B. & Mann J. J., Risk factors for suicidal behavior: utility and limitations of research instruments. In M.B. First [Ed.] Standardized Evaluation in Clinical Practice, pp. 103-130, 2003.)

For reprints of the C-SSRS contact [name]., New York State Psychiatric Institute, [name]; inquiries and training requirements contact [contact]

© 2008 The Research Foundation for Mental Hygiene, Inc.

SUICIDAL IDEATION				
Ask questions 1 and 2. If both are negative, proceed to "Suicidal Behavior" section. If the answer to question 2 is "yes", ask questions 3, 4 and 5. If the answer to question 1 and/or 2 is "yes", complete "Intensity of Ideation" section below.		time	Past 6 Months	
1. Wish to be Dead Subject endorses thoughts about a wish to be dead or not alive anymore, or wish to fall asleep and not wake up. Have you thought about being dead or what it would be like to be dead? Have you wished you were dead or wished you could go to sleep and never wake up? Do you ever wish you weren't alive anymore? If yes, describe:	Yes	No	Yes	No
2. Non-Specific Active Suicidal Thoughts General, non-specific thoughts of wanting to end one's life/commit suicide (e.g., "T've thought about killing myself") without thoughts of ways to kill oneself/associated methods, intent, or plan during the assessment period. Have you thought about doing something to make yourself not alive anymore? Have you had any thoughts about killing yourself? If yes, describe:	Yes	No	Yes	No

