3. Active Suicidal Ideation with Any Methods (Not Plan) without Intent to Act Subject endorses thoughts of suicide and has thought of at least one method during the assessment period. This is different than a specific plan with time, place or method details worked out (e.g., thought of method to kill self but not a specific plan). Includes person who would say, "I thought about taking an overdose but I never made a specific plan as to when, where or how I would actually do it and I would never go through with it." Have you thought about how you would do that or how you would make yourself not alive anymore (kill yourself)? What did you think about?	Yes	No	Yes	No
If yes, describe:				
4. Active Suicidal Ideation with Some Intent to Act, without Specific Plan Active suicidal thoughts of killing oneself and subject reports having some intent to act on such thoughts, as opposed to "I have the thoughts but I definitely will not do anything about them." When you thought about making yourself not alive anymore (or killing yourself), did you think that this was something you might actually do? This is different from (as opposed to) having the thoughts but knowing you wouldn't do anything about it.	Yes	No	Yes	No
If yes, describe:				
5. Active Suicidal Ideation with Specific Plan and Intent Thoughts of killing oneself with details of plan fully or partially worked out and subject has some intent to carry it out. Have you ever decided how or when you would make yourself not alive anymore/kill yourself? Have you ever planned out (worked out the details of) how you would do it? What was your plan? When you made this plan (or worked out these details), was any part of you thinking about actually doing it?	Yes	No	Yes	No
If yes, describe:				
INTENSITY OF IDEATION				
The following feature should be rated with respect to the most severe type of ideation (i.e., 1-5 from above, with 1 being the least severe and 5 being the most severe). Most Severe Ideation:		ost	Most Severe	
Type # (1-5) Description of Ideation Frequency				
How many times have you had these thoughts? Write response (1) Only one time (2) A few times (3) A lot (4) All the time (0) Don't know/Not applicable	_	_		_

© 2008 Research Foundation for Mental Hygiene, Inc.

C-SSRS-Children's Baseline/Screening (Version 6/23/10)

Page 1 of 2

SUICIDAL BEHAVIOR (Check all that apply, so long as these are separate events; must ask about all types)			Lifetime	

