1 INTRODUCTION

The purpose of this statistical analysis plan (SAP) is to ensure the credibility of the study findings by specifying the statistical approaches to the analysis of the data. This SAP covers the planned analyses of all data collected on the eCRFs, and will identify handling of data issues. The statistical analysis plan presented in this document will supersede the statistical analysis methods described in the clinical protocol. Any deviations/changes from the planned analyses described in this SAP will be identified, with justification, in the appropriate section of the clinical study report. This SAP is based on the clinical study protocol 810P204, version 3.0, dated 12 Apr 2019 and its associated electronic case report forms (eCRF).

2 **STUDY OBJECTIVES**

The primary objective is to evaluate the effect of SPN-810 treatment on brain activity in subjects aged 8-12 years with ADHD and IA using functional Magnetic Resonance Imaging (fMRI).

Secondary objectives are to evaluate the effect of SPN-810 treatment on:

- The functional connectivity between brain regions using resting-state fMRI (rs-fMRI)
- The concentration of neurotransmitters glutamate and gamma-aminobutyric acid (GABA) using Magnetic Resonance Spectroscopy (MRS)
- Safety of SPN-810

Tertiary objectives are to evaluate the following:

- Pharmacokinetics (PK) of Molindone
- Effect of SPN-810 treatment on the Clinical Global Impression-Severity (CGI-S) and -Improvement (CGI-I) scores
- Effect of SPN-810 on the Retrospective-Modified Overt Aggression Scale (R-MOAS) score.

3 **ENDPOINTS**

Primary Endpoint is the change in the whole brain in BOLD fMRI contrast in response to the PSAP task from Baseline (Visit 2) to Visit 5.

Secondary Endpoints are:

- Change in functional connectivity as reflected in the Fisher's Z-transformation of correlation coefficients between brain regions during rs-fMRI from Baseline (Visit 2) to Visit 5.
- Change in the concentrations of neurotransmitters GABA and glutamate in the anterior cingulate cortex (ACC) from Baseline (Visit 2) to Visit 5 as determined by MR spectroscopy.
- Safety endpoints:
 - 1) Adverse events.
 - 2) Safety scales (Simpson-Angus Scale, Barnes Akathisia Rating Scale [BARS], and Abnormal Involuntary Movement Scale [AIMS]).
 - 3) Clinical laboratory tests (hematology, chemistry, and urinalysis).

- 4) Vital signs.
- 5) Electrocardiograms (ECGs).
- 6) Columbia-Suicide Severity Rating Scale (C-SSRS).

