7.6.5 Physical Examinations

Findings from the physical examinations will be listed for each system or area examined.

7.6.6 *C-SSRS*

C-SSRS outcomes will be summarized using number and percent of subjects by categories for suicidal ideation only, suicidal behavior only, and suicidality (ideation and behavior combined). The summary will be presented by treatment group.

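### The planned C-SSRS summary puts all five ideation levels in one category with no Visit 1 comparison, so the by-arm table shows neither how severe ideation was nor whether it worsened in a child admitted at level 1

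*Protocol*

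**What the plan says.** Protocol 8.3.7 reports numbers and percentages of subjects "by categories for suicidal ideation only, suicidal behavior only, and suicidality (ideation and behavior combined", by treatment group, and adds a test against placebo. SAP 7.6.6 drops the test and otherwise repeats the rule: "C-SSRS outcomes will be summarized using number and percent of subjects by categories for suicidal ideation only, suicidal behavior only", and the combined category. The SAP governs, because its Introduction says that it "will supersede the statistical analysis methods described in the clinical protocol". Neither section names an ideation level, a worst level, a change from Visit 1 or a count of worsening.

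The instrument is finer than that. In Protocol 12.6.1 ideation is rated "1-5 from above, with 1 being the least severe and 5 being the most severe". Level 1 is described as "Subject endorses thoughts about a wish to be dead or not alive anymore, or wish to fall asleep and not wake up"; level 5 is headed "Active Suicidal Ideation with Specific Plan and Intent". The Since Last Visit form (12.6.2) uses the same five levels. Protocol 6.3.9.4 gives the Baseline form at Visit 1 and the Since Last Visit form at Visits 4 and 6.

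Exclusion 8 (Protocol 4.1.2) bars "active suicidal plan/intent or active suicidal thoughts in the 6 months before the Screening Visit or more than 1 lifetime suicide attempt". A passive wish to be dead is not listed.

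**The concern.** The C-SSRS is a named safety endpoint in both documents. For such an endpoint the useful questions are whether suicidal thinking appears after entry, how severe it becomes, and whether it exceeds what the child reported at entry. The planned table answers only the first, and only for a child who entered with none.

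The plan treats its other safety measures differently. SAP 7.6.2 has shift tables for laboratory values, SAP 7.6.3 and 7.6.4 report change from baseline for vital signs and ECG, and SAP 7.6 and 7.6.7 look for worsening or change on the extrapyramidal scales. The C-SSRS is graded and has a Visit 1 assessment, yet no comparison with Visit 1 is planned.

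The combined category adds a second uncertainty. It may mean ideation and behavior together, or either one, and the two readings count different children.

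**Working it through.** The plan gives no figure to reproduce. The check maps each ideation level to the planned categories, for a child with no suicidal behavior.

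**Inputs.** Ideation levels 0 (none) to 5, from Protocol 12.6.1 and 12.6.2. Categories from SAP 7.6.6. Entry rule from exclusion 8. Visit days from Protocol Table 1.

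**1. Admissible starting levels.** The Baseline form labels levels 2 to 5 as active thoughts or ideation. Exclusion 8 bars active thoughts in the 6 months before screening. On the form's past-6-months column, the levels that exclusion 8 leaves open are therefore 0 and 1.

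**2. Upward moves from those levels.**

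| Move | Number | Category before | Category after | Category changes? |
|---|---|---|---|---|
| 0 to 1, 2, 3, 4 or 5 | 5 | none | ideation only | yes |
| 1 to 2, 3, 4 or 5 | 4 | ideation only | ideation only | no |

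Total: 5 + 4 = 9 upward moves. Hidden: 4 of 9 (44%), and 4 of 4 from level 1. These count kinds of move, not children; the documents do not say how many children enter at level 1.

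**3. Severity among new cases.** The five moves from level 0 do change category, but all land in the same cell. A child who newly reports a wish to be dead is counted exactly like one who newly reports plan and intent.

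**4. Which responses the table counts.** SAP 7.6.6 does not say whether Visit 1 responses are included. If they are, a level-1 child is already in the ideation category before treatment. If they are not, the child is counted once ideation is endorsed again, at whatever level. The level is lost either way.

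**5. The combined category.** Let a, b and c be the numbers with ideation only, behavior only and both. Read as *and*, the category holds c; read as *or*, it holds a + b + c. The readings differ by a + b.

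**6. With levels and a shift table.** All 9 moves show, including the 4 from level 1.

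**7. Recall windows.** Visit 1 (past-6-months column): 6 months. Visit 4, since Visit 1: up to 21 − (−30) = 51 days, partly before the first dose. Visit 6, since Visit 4: 35 − 21 = 14 days. Later windows are much shorter than the Visit 1 window.

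**The case against.** A reader might infer that the plan reports a worsening child as unchanged. It does not: no C-SSRS change or by-visit table is planned, so nothing carries that label. The child is counted in a broad category.

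A reader might also infer that worsening would be invisible in the trial. That goes too far. SAP 6.1 plans subject data listings, and in a study of about 30 children individual cases can be read, although no C-SSRS listing is named. Protocol 6.3.1 makes exacerbation of an existing disease an adverse event, 6.3.2 makes important medical events serious, and SAP 7.6.1 tabulates treatment-emergent events by severity. New plan and intent could appear there if the investigator records it. These routes stand as mitigation, but they depend on individual reporting and do not repair the by-arm C-SSRS summary.

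Nor is a rise within ideation the only change open to a level-1 child. Progression to behavior changes the category, and reporting nothing later leaves it. Counting rises that start at levels 2 to 4 would enlarge the problem wrongly, since exclusion 8 bars those levels on the past-6-months column.

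Admission at level 1 is by omission. The Visit 1 screen (Protocol 6.3.9.4) and exclusion 18 leave discretion to exclude such a child. This makes the frequency unknown; it does not close the gap.

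Finally, the phrase about categories for ideation could be read as allowing sub-levels. Neither document names any, so the table programmer has nothing to work from.

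**Conclusion.** The point holds for the by-arm summary. It cannot distinguish a passive wish to be dead from ideation with plan and intent in any child, and it cannot show a rise within ideation in a child admitted at level 1: 4 of 4 moves from that level, 4 of 9 from the admissible levels.

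The count assumes that the reference is the past-6-months column of the Visit 1 form, that exclusion 8 is applied as written, and that the child has no suicidal behavior. The plan does not say whether the lifetime or past-6-months column is the baseline.

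The severity is minor. The study planned about 30 children, and SAP 6.1 states that it ended early and that all analyses are descriptive. No test or primary result depends on this table. Under those conditions, though, a single case is informative only if its level can be read.

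**What to change.** In SAP 7.6.6, present by arm:

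- n (%) at each worst post-baseline ideation level, 0 to 5;
- a shift table of that level against the Visit 1 past-6-month level, with n (%) whose post-baseline level is higher than at Visit 1;
- n (%) with any suicidal behavior;
- n (%) with suicidality, defined as ideation or behavior.

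The cost is a few lines of SAP text and one table. The item-level responses are already collected at Visits 1, 4 and 6, and nothing changes in conduct or eligibility. If the SAP is already final, its Introduction provides for a justified change to be reported in the clinical study report.

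Two limits should be stated with the table. First, cells will be sparse: 2 admissible starting levels × 6 post-baseline levels = 12 cells per arm, against 15 children per arm planned in Protocol 4.1. Second, the Visit 1 column looks back 6 months and the later forms only weeks, so the shift table leans toward apparent improvement. Readers should use the upward shifts and the worst level, and should not interpret the downward shifts. Because the Visit 4 window can begin before the first dose, the columns should be labeled post-baseline, not on-treatment.
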